## Secondary measurements

Secondary Mechanical Ventilation measurements will be PIP, Expired Vt, RR, MV, EtCO2. Hemodynamic measurements will include Arterial Blood Pressure (Systolic, Diastolic, Mean), and Heart Rate. Blood gas data Measurements will be pH, PO2, PCO2, SPO2 and PO2/FiO2.

## Time points of measurements

After a stabilization period of 1-2 minutes of Mechanical Ventilation (stabilization defined as a stable Vt for at least 4 consecutive breaths), the above parameters (except Blood gas measurements – see Appendix 6) will be measured at the following time points:

T1	Baseline	After tracheal intubation and ventilation stabilization, with the patient in the supine position and before surgical incision
T2	Pneumoperitoneum	After insufflating CO 2 to the defined IAP
T2c	Correction	After adjusting PIP to return Vt to 6-7 ml/kg IBW or within 10% of baseline
T3	Trendelemburg	After Trendelemburg positioning
T3c	Correction	After Trendelemburg positioning and after adjusting PIP to return Vt to 6-7 ml/kg IBW or within 10% of baseline
T4	Deflation	After completing the laparoscopic procedure with the patient returned to the supine position with the abdomen deflated
T4c	Correction	Post-deflation correction, after returning PIP to baseline
T5	After RM / Before Reversal of Neuromuscular Blockade	3 minutes after RM in the RM group and before the reversal of neuromuscular blockade and Extubation in both groups
T6	Post-operative	30 min after the admission in PACU

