#### Recruitment Maneuver (Time and Method of RM)

After deflation of pneumoperitoneum, patients in Control group will continue to be ventilated with the same ventilation settings while RM will be performed to patients in RM group.

Since the locally available Anesthesia Workstation does not permit CPAP > 20 cm H2O, RM will be performed by setting Manual / Spontaneous Ventilation Mode and by setting Adjustable Pressure Limitation (APL) Valve to 30 cm H2O for 30 seconds (Fresh Gas Flow: 5 lt/min, FiO2 0,4), measured by operating room digital clock, while monitoring the patient for signs of adverse effects, such as hemodynamic instability.

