## Measurements

### Primary endpoint

The improvement of  $Com_{dyn}$  will be the primary endpoint of the study.  $Com_{dyn}$  will be measured automatically by the Dräger Primus Anesthesia workstation (SW 4.5n).  $Com_{dyn}$  is determined from  $P_{plateau}$  and Expiratory Tidal Volume and is equal to the measured Total Compliance [ $V_t / (P_{plateau} - PEEP)$ ] minus the System and Hose Compliance determined in the Self-Test of the workstation. Weight-corrected  $Com_{dyn}$  will be calculated by dividing  $Com_{dyn}$  by the weight of patient in kilograms ( $Com_{dyn-wc} = Com_{dyn} / \text{weight}$ ). Time points of measurements are defined below.

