## End of Treatment

The treatment (RM) will start 3 minutes after the Pneumoperitoneum deflation and will last for 30 seconds.

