## Statistical Methods

### Sample size determination

Power Analysis will be conducted for determination of the Sample Size of this study, in order to estimate a Sample Size that is required so that the study would have adequate power to detect clinically meaningful differences between the two groups, especially concerning Lung Compliance (which is the primary outcome of the study).

For this analysis, we used G\*Power Software (version 3.1.9.2), which is freely available at <http://www.gpower.hhu.de/en.html> from the Heinrich-Heine-Universität of Dusseldorf.

Our Power Analysis is based on a published study in literature, from Manner et al. Assuming that Clinically meaningful difference between the two groups is 20% of the mean value and SD of the observed Lung Compliance is 15% of the mean value, therefore Size effect = 0.2 /

0.15 = 1.33, with two-sided testing, with alpha = 0.05 and power = 0.9 (therefore,  $b = 1 - \text{power} = 0.1$ ). Under these assumptions, G\*Power calculated that we will need minimum 13 patients in each group (totally, 26 subjects) for this study to have adequate power.

Assuming a 15% drop-out rate of the initial number of subjects enrolled to this trial, total number of **30** patients will have to be randomized

Alternatively, using the adequate mathematic formula (see Appendix 2) and the results from the Manner et al study, we confirm a minimum Sample Size of 26 patients.

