### Statistical Analysis

[figure not shown]
Investigators will assess data for normality (using Kolmogorov Smirnov and Shapiro Wilks test). Ventilatory and hemodynamic data and intraoperative and postoperative variables (all continuous variables) will be presented as mean values (+/- SD). Data will be compared between and within groups using Mixed Analysis of Variance (Mixed Anova - General Linear Model) if are normally distributed or with Kruskal Wallis test in case that we do not have normally distributed data. Bonferroni correction will be used for multiple comparisons correction. In order to check and supplement our Mixed Analysis of Variance we will also use two-sample t-test to compare the two groups at each time point (for ventilatory and hemodynamic variables). Patient and procedural characteristics will be compared between groups using independent-sample t-test for continuous variables and chi-square test for categorical variables. Two tailed P-values < 0.05 will be considered statistically significant. For data analysis, the investigators will use SPSS statistical software (version 22).

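### T5, the only compliance reading after the recruitment manoeuvre, has a fixed elapsed time in the RM arm but none in the control arm, so time since deflation may differ between the groups.

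*Protocol*

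**What the plan says.** The table in Protocol, Time points of measurements, defines T5 in one row for both groups: "3 minutes after RM in the RM group and before the reversal of neuromuscular blockade and Extubation in both groups". The first condition applies to the RM arm alone. The second applies to both arms but only says what T5 must precede.

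Protocol, End of Treatment, fixes the manoeuvre itself: "The treatment (RM) will start 3 minutes after the Pneumoperitoneum deflation and will last for 30 seconds". The Abstract gives the same start. For the other arm, Protocol, Recruitment Maneuver (Time and Method of RM), says only that "patients in Control group will continue to be ventilated with the same ventilation settings". It describes no waiting period or matched interval.

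Improvement in dynamic compliance "will be the primary endpoint of the study" (Protocol, Primary endpoint), with no time point named as primary. Appendix 4, the form on which compliance is entered, ends at T5. Appendices 5 and 6 (hemodynamics and blood gases) continue to T6, which is set at 30 minutes after PACU admission in both arms. Under Statistical Analysis, a mixed ANOVA is supplemented by group comparisons at single points: "we will also use two-sample t-test to compare the two groups at each time point".

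**The concern.** A comparison of two arms at a named time point assumes that the point means the same thing in each. Here the RM arm is read at a set interval after deflation, and the control arm at any moment up to reversal. If compliance or blood gases are still changing after deflation, a difference in elapsed time adds to, or subtracts from, the difference attributed to the manoeuvre.

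The protocol gives reason to think these outcomes move with time. It describes CO2 absorption that raises arterial CO2 into the postoperative period, atelectasis that develops under anesthesia and lowers compliance, and an influence of pneumoperitoneum duration and positioning on mechanics and gases.

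Two features make the gap harder to dismiss. First, the envelope is opened at deflation, and the unblinded Principal Investigator is one of the anesthesiologists, so the open control window runs while someone in the room knows the allocation. Second, Appendices 3 to 6 have no field for the clock time of deflation, T4c or T5. A difference in timing could not be detected or modelled from the study forms, and adjusting for T1 or T4c values cannot remove a shift that arises after T4c.

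**Working it through.** **1. Elapsed time at T5, from the text**

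- RM arm: 3 min (deflation to start of manoeuvre) + 0.5 min (duration) + 3 min (manoeuvre to T5) = 6.5 min after deflation. This counts the last 3 minutes from the end of the manoeuvre. Counted from its start, the sum is 3 + 3 = 6.0 min.
- Control arm: no sum can be formed. T5 follows T4c in the table and must precede reversal. Any time in that interval satisfies the protocol, including 6.5 min.

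**2. Which readings depend on T5**

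- Compliance: T5 is the only reading after the manoeuvre (Appendix 4).
- Blood gases: T5 and T6 (Appendix 6). T6 has the same anchor in both arms.
- The comparison of T5 with baseline within the RM group does not involve control timing and is untouched.

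**3. The plan's own sample size, reproduced**

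Inputs from Sample size determination: a target difference between groups of 20%, and a standard deviation of 15%, both relative to mean compliance; two-sided alpha 0.05; power 0.90. Standardized effect d = 0.20/0.15 = 1.333. For a two-sample t-test with n per group, the noncentrality is d × √(n/2) with 2n − 2 degrees of freedom.

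- n = 12: power 0.877
- n = 13: power 0.903
- n = 15: power 0.941

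The stated minimum of 13 per group is confirmed. The timing question does not change it.

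**4. What a timing shift would do (illustration)**

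The documents give no rate of change of compliance after deflation and no typical time to reversal, so the shift b is an assumption, in percent of mean compliance. With 15 per group and SD 15%, the rejection rate with no true effect uses d = b/15. Power with a true 20% effect and a shift against RM uses d = (20 − b)/15.

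| Shift b | d, no true effect | False-positive rate | d, true effect 20% | Power |
|---|---|---|---|---|
| 0% | 0 | 5.0% | 1.333 | 94.1% |
| 2% | 0.133 | 6.4% | 1.200 | 88.7% |
| 5% | 0.333 | 14.3% | 1.000 | 75.3% |
| 10% | 0.667 | 42.2% | 0.667 | 42.2% |

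**5. What would produce such a shift**

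Shift = drift per minute × gap in minutes. If drift were 0.25% to 1% per minute (assumed), a gap of 0 min gives 0%, a gap of 5 min gives 1.25% to 5%, and a gap of 15 min gives 3.75% to 15%. The largest value needs the fastest drift and the longest gap together. The sign depends on whether compliance is recovering or deteriorating during that period, which the documents do not say.

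**The case against.** The strongest reply is that the protocol implies a parallel sequence. Randomization and Blinding Procedure both refer to the moment when the manoeuvre is applied or not applied, as if controls had an equivalent slot. The Second Investigator then enters and records from the monitor. The T5 row is shared and has a shared limit. After deflation both arms are supine, with PIP returned to baseline at T4c and the same ventilation strategy, which may keep any drift small. On this reading only the wording is incomplete.

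Much of this stands. It makes a common schedule plausible and rules out several stronger readings:

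- A reader might infer that the arms are measured at different times and that time is confounded with treatment. The text leaves control timing open; it does not show a difference.
- A reader might infer that control T5 depends on wound closure or on the Principal Investigator's choice. Wound closure is not mentioned, and recording is assigned to the Second Investigator. Influence by the unblinded anesthesiologist is possible but is not stated.
- A reader might take T5 as the declared primary time point. It is decisive only because no later compliance reading exists.
- A reader might extend the whole argument to blood gases, but these also have T6 with a common anchor.

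The reply does not supply a time. The control slot has no stated start, length or elapsed time. The section that comes closest, Blinding Procedure, labels the recording after the manoeuvre as T4, whereas the time-point table defines T4 as deflation. The two sections need to be reconciled.

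**Conclusion.** The point holds as a possible bias, not a demonstrated one. T5 is anchored at about 6.5 minutes after deflation in the RM arm (6.0 if the interval is counted from the start of the manoeuvre) and is bounded only from above in controls. Because it is the sole compliance reading after the manoeuvre, any difference in elapsed time would pass directly into the between-group result for the primary endpoint and into the T5 blood gases. The size and direction cannot be derived from the documents. The false-positive and power figures above show only how sensitive a trial with 15 per group would be to an assumed shift, and a shift of zero is compatible with the protocol. Sample size is not affected.

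This should be fixed. It is a measurement definition in the protocol's own table, it costs almost nothing to settle before enrolment, and the study forms would not allow a correction afterwards.

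**What to change.** - Define T5 at one elapsed time after deflation in both arms. For controls this is the time that matches 3 minutes after the end of the RM slot, about 6.5 minutes after deflation, before reversal. State whether the 3 minutes run from the start or the end of the manoeuvre.
- Add fields to the data forms for the actual clock times of deflation, T4c and T5 in every patient, so that adherence can be reported by arm.
- Reconcile the T4 label in Blinding Procedure with the time-point table, so that it is clear when the Second Investigator enters and which point is being recorded.

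The cost is one line in the table, one corrected label and three time fields. Only the timing of a measurement changes; treatment, number of patients and procedures stay as they are.

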## Follow up measurements

There will be a postoperative follow up for all patients participating in our study, concerning, among other, signs and symptoms of respiratory failure. Respiratory failure practically means the need for invasive or non-invasive ventilation after extubation. In such case, we should define the pulmonary pathophysiology involved, i.e. pneumonia, atelectasis, pulmonary embolism, pneumothorax, acute lung injury (ALI), asthma, non-cardiogenic pulmonary edema and severe hypercapnia. The routine postoperative oxygen will be applied for 30 minutes postoperatively and will also be noted.

## End of Treatment

The treatment (RM) will start 3 minutes after the Pneumoperitoneum deflation and will last for 30 seconds.

## End of Study

The patients will be monitored throughout the operation and in the postoperative period too, in PACU and in Pediatric Clinic (see also the measurements section - primary endpoint, secondary measurements and follow up). Patients will be followed up during their hospital stay, the length of which will be recorded. Possible adverse events during the hospital stay will also be recorded.

## Efficacy and Safety Issues

The efficacy of the RM to improve  $Com_{dyn}$  and gas exchange is the main issue of this study. The investigators regard that  $Com_{dyn}$  will be statistically significantly improved in the RM group compared to Control group. In this study, we consider clinically significant a 20% increase in the weight corrected mean  $Com_{dyn}$  in the RM group.

This improvement in lung compliance maybe would not be clinically significant, as our study population consists of healthy children (children with ASA I-II classification). Nevertheless, the possibility of underlying comorbidities should always be taken into account and anesthesia in addition to these comorbidities could negatively influence cardiovascular and pulmonary function, and thus patients' outcome. This is the reason that ventilation strategy adopted in this study has a protective-lung ventilation strategy orientation, with lower  $V_t$  and higher PEEP than usual in clinical practice the past years.

The investigators regard that there would be statistical significant difference within RM group, as well.  $Com_{dyn}$  is expected to be significantly improved in post-RM measurements in comparison to baseline  $Com_{dyn}$ , for the patients of RM group. A 20% increase in  $Com_{dyn}$  would be clinically significant too.

Secondarily, the investigators regard that RM will improve post-RM intra- and post-operative  $PO_2$  and ratio  $PO_2/FiO_2$ . For the population of this study (children ASA I-II), this improvement may also not have a clinically significant impact.

Although recruitment procedures are generally well tolerated with few adverse effects, there are several potential complications that could occur.

Because of the transient increase in intrathoracic pressure and consequent reduction in venous return, cardiac output may be impaired, producing hypotension – a complication that appears to be more common in patients with poor chest wall compliance and limited oxygenation response from recruitment. Generally, hypotension during the maneuver suggests relative volume depletion. In this study, RM will be performed with a parallel beat-to-beat hemodynamic monitoring (Invasive Arterial Blood Pressure Monitoring). Patients with severe hemodynamic instability (hypotension or arrhythmias) will be removed from the study, as already mentioned. In these patients, the removal of RM is expected to improve arterial blood pressure – in case hypotension persists, vasoconstrictors (ephedrine, norepinephrine) will be administered in adequate for each patient doses.

A decrease in cerebral perfusion pressure has been noted as a RM complication, which may contraindicate this procedure in head injured patients. In this study, patients with history of severe brain injury and intracranial hypertension meet the exclusion criteria and will be excluded.

Barotrauma, including pneumothorax and pneumomediastinum, has been also described but the exact risk remains unclear. Nevertheless, when RM is performed with the duration and the pressure levels adopted in this study (Sustained Inflation with CPAP 30 mm  $H_2O$  for 30

seconds) is thought to be a safe clinical maneuver without such major complications to children

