### Results and Discussion

Data will be presented as mean value (+/- SD) and  $p < 0.05$  will be considered significant. The investigators will use Mixed Analysis of Variance to make comparisons between and within groups. At time points before RM is performed, there should be no significant differences in Lung Compliance between the two groups ( $p > 0.05$ ). The investigators will use two-sample t-test as supplementary analysis in order to compare the two groups at each time point, while chi-square test for categorical variables and two-sample t-test for continuous variables for patient and procedural characteristics differences between the two groups will be used. In the RM group, according to similar studies, we expect to detect a significant increase in lung Compliance after RM in comparison to control group where RM will not be applied. In the RM group, the investigators estimate that Dynamic Lung Compliance will be significantly increased compared to baseline compliance too. There should be no significant differences in demographics between the two groups. The investigators expect that there will be no statistical or/and clinical significant differences in patients' hemodynamics and blood gas measurements.

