### Limitations of the study

This study is aimed to demonstrate a restoration in  $Com_{dyn}$  and gas exchange by the RM. It will not be powered to describe overall pulmonary outcomes, such as postoperative atelectasis or lung infection.

Lung mechanics include a variety of properties approaching lung function in a spherical way; this study, however, is limited to  $Com_{dyn}$  – as an easily accessible parameter in everyday clinical practice.

Our study population will be healthy and heterogeneous in terms of age and therefore size. Although  $Com_{dyn}$  will be adjusted by weight,  $Com_{dyn}$  may be affected by other factors related to age, such as compliance of the chest wall and resistance of the airways. In addition, both the ventilator used and the measurement technique used to obtain  $Com_{dyn}$  could also affect our results.

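### The 20% rise over pre-incision baseline within the RM arm is offered as a sign of efficacy, but it is not the RM effect and not the between-group 20% the trial is sized for

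*Protocol*

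**What the plan says.** Protocol, *Efficacy and Safety Issues*, opens with the randomised comparison: compliance should improve in the RM group relative to control, and a 20% increase is named as clinically significant. A later paragraph of the same section adds that "there would be statistical significant difference within RM group, as well", that for RM patients compliance "is expected to be significantly improved in post-RM measurements in comparison to baseline", and that a 20% increase "would be clinically significant too". The abstract (*Results and Discussion*) repeats the expectation without a threshold: "Dynamic Lung Compliance will be significantly increased compared to baseline compliance too".

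*Time points of measurements* defines baseline, T1, as "After tracheal intubation and ventilation stabilization, with the patient in the supine position and before surgical incision". Pneumoperitoneum (T2), Trendelenburg positioning (T3), deflation (T4) and the pressure corrections (T2c, T3c, T4c) all come before T5, the post-RM reading.

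*Sample size determination* uses a different contrast: "Clinically meaningful difference between the two groups is 20% of the mean value".

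**The concern.** A change from T1 to T5 in one arm has no concurrent comparator. The protocol's introduction (*Pulmonary Function during Laparoscopy*) says that pneumoperitoneum lowers compliance and that respiratory mechanics depend on its duration and on positioning. Whatever remains of those influences at T5 enters the within-arm change together with the RM effect, and only the control arm can separate the two.

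The same figure of 20% is attached to both contrasts. A report that follows the text could therefore deny a clinically significant improvement although the RM achieved its planned effect. It could also assert one because of a rise that controls shared. In either case the statement would not rest on the randomisation.

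**Working it through.** **The planned figure.** Inputs from *Sample size determination*: difference 20% of the mean between groups, SD 15% of the mean, two-sided alpha 0.05, power 0.90.

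- Effect size d = 0.20 / 0.15 = 1.33.
- Two-sample noncentral t: power 0.877 at 12 per arm and 0.903 at 13 per arm. The stated 13 per arm reproduces.
- At the 15 per arm to be randomised, power is 0.941.

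This calculation concerns RM versus control only. No within-arm change is sized.

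**What the within-arm change measures.** Let T1 have the same expected value in both arms, as randomisation implies. Let r be the fraction by which control compliance at T5 lies below T1. The documents do not give r, so it is assumed and ranged. If the RM delivers exactly 20% over control at T5:

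- RM-arm T5/T1 = 1.2 × (1 − r)
- RM effect over control needed to reach 20% above T1 = 1.2 / (1 − r) − 1

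| r (assumed) | RM-arm T5 versus T1 at the planned effect | RM effect over control needed for +20% versus T1 |
|---|---|---|
| 0% | 1.2 × 1.00 = 1.20, +20% | 20% |
| 5% | 1.2 × 0.95 = 1.14, +14% | 26% |
| 10% | 1.2 × 0.90 = 1.08, +8% | 33% |
| 15% | 1.2 × 0.85 = 1.02, +2% | 41% |
| 20% | 1.2 × 0.80 = 0.96, −4% | 50% |

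The two 20% figures agree only at r = 0.

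**The other direction.** Suppose the RM has no effect and both arms end above T1. Take n = 15 and an SD of the paired difference of 15% × √(2(1 − ρ)), where ρ is the within-patient correlation (also not given). For ρ = 0, 0.5 and 0.7 this SD is 21.2%, 15.0% and 11.6%. A paired t-test at two-sided 0.05 then shows a significant rise with these probabilities:

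- shared rise of 5%: 13%, 22% and 34%
- shared rise of 10%: 40%, 67% and 87%

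The nominal rate in that direction is 2.5%. These figures show how the test behaves if such a rise exists. Nothing in the protocol says that it does.

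**The case against.** The strongest reply is that this is an added expectation and not a decision rule. The text speaks of what the investigators regard, estimate or expect, and it puts RM versus control first. The trial is sized on that contrast. *Statistical Analysis* plans a mixed ANOVA with Bonferroni correction and two-sample tests at each time point. The efficacy section also concedes that the improvement may not matter clinically in healthy children. All of this stands. A reader might infer that the within-arm change is a formal success criterion or that the primary comparison is compromised; the protocol supports neither.

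Three other strong readings also fail:

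- **Several rival 20% targets.** The first 20% statement in the efficacy section directly follows the comparison with control and can be read that way. The abstract gives no threshold. The limitations section says "This study is aimed to demonstrate a restoration in" compliance and gas exchange, but attaches no figure.
- **False success when controls merely recover.** Recovery to T1 is a zero change. A spurious rise needs controls to end above T1.
- **A known direction of bias.** The protocol describes loss of compliance during pneumoperitoneum. If some of that loss persists to T5, the within-arm change understates the RM effect. The documents do not say how much persists.

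It can also be said that the ranking of within-arm contrasts belongs in a statistical analysis plan. Here, however, the protocol itself attaches a 20% mark to the uncontrolled change, and a later plan would inherit it.

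**Conclusion.** The point holds as a flaw of interpretation in a secondary statement. The RM-arm change from T1 to T5 mixes the RM effect with the course of anaesthesia, pneumoperitoneum, positioning and deflation, and its 20% mark is a different quantity from the 20% the trial is sized for. With an assumed residual loss of 5% to 15% in controls, an RM with the full planned effect ends 14% to 2% above T1 and misses the mark. Meeting it would take an RM effect of 26% to 41% over control.

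The size depends on control drift, which the documents do not report, and so does the direction of any error. Power for the between-group comparison (0.903 at 13 per arm) is not touched.

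**What to change.** - In *Efficacy and Safety Issues*, state that the 20% means RM versus control in mean weight-corrected dynamic compliance at T5, and delete the 20% mark for the within-arm change.
- There and in the abstract's *Results and Discussion*, state that change from baseline within the RM arm is descriptive and not evidence of efficacy. The within-group terms of the mixed ANOVA may still be reported on that footing.
- If return to baseline is of interest, compare the ratio T5/T1 between arms, with a confidence interval.

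The cost is wording in two sections. No extra patients or measurements are needed, because the Appendix 4 record already has compliance at T1 and T5 for every patient. The sponsor gives up a secondary, uncontrolled efficacy statement.

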## Removal of Patients from Therapy

Hemodynamic instability during the RM will be the main cause for removing patients from therapy, defined as persistent Hypotension (SBP <70 mm Hg in those 1–4 years, <80 mm Hg in those 5–12 years, and <90mm Hg in those >12 years). Hypoxemia (oxygen saturation <92%), bradycardia (heart rate <80 bpm in those <2 years, <60 bpm in those > 2 years) or arrhythmias will also impose the removal of RM and application of therapeutic measurements in case the symptoms insist.

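### Unstable children are removed from therapy in one section and from the study in another; the second reading takes patients out of the RM arm only, after allocation

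*Protocol*

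**What the plan says.** **Two rules for the same event.** Protocol, Removal of Patients from Therapy: "Hemodynamic instability during the RM will be the main cause for removing patients from therapy, defined as persistent Hypotension", with age-specific pressure limits. Hypoxaemia, bradycardia "or arrhythmias will also impose the removal of RM and application of therapeutic measurements in case the symptoms insist". Both sentences concern the treatment. Protocol, Efficacy and Safety Issues, goes further: "Patients with severe hemodynamic instability (hypotension or arrhythmias) will be removed from the study, as already mentioned".

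**Who can be affected.** Under Recruitment Maneuver, "patients in Control group will continue to be ventilated with the same ventilation settings while RM will be performed to patients in RM group". The intraoperative complication exclusions under Exclusion Criteria run from induction to deflation and apply to both groups. Under Randomization, the envelopes stay closed until deflation, just before the RM.

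**Which patients are analysed.** Data Presentation Plan, Flow chart, uses a per-protocol analysis if the great majority complete. If many do not, it uses intention to treat with last observation carried forward (LOCF). Neither term has a threshold.

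**Who is expected to become unstable.** Efficacy and Safety Issues calls hypotension "a complication that appears to be more common in patients with poor chest wall compliance and limited oxygenation response from recruitment".

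**What is recorded.** The first scheduled measurement after the RM is T5, "3 minutes after RM in the RM group and before the reversal of neuromuscular blockade and Extubation in both groups". The haemodynamic form (Appendix 5) goes from T4c to T5. The section on Adverse Events requires RM complications and any perioperative event to be recorded, and names hypotension, bradycardia and desaturation. Vasoconstrictor need is on the Appendix 3 form and in Table 1.

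**The concern.** Stopping a maneuver and discarding a randomised child's data are different decisions, and the protocol treats them as one. If the child leaves the study, the RM group at T5 holds only those who tolerated the RM, while the control group holds everyone who reached deflation. Randomisation no longer protects that comparison. If tolerance is related to compliance, the primary endpoint shifts towards the RM.

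The same event is also the main safety outcome of a trial that calls itself a safety and efficacy study. The scheduled pressures at T4c and T5 lie on either side of the 30-second RM. They could agree between groups even if pressure fell and recovered in between. The abstract's expectation that "there will be no statistical or/and clinical significant differences in patients' hemodynamics and blood gas measurements" could therefore appear to be met without the exposure period having been compared.

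**Working it through.** **1. The texts side by side.**

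| Section | What is removed |
|---|---|
| Removal of Patients from Therapy, persistent hypotension | the patient, from therapy |
| Removal of Patients from Therapy, hypoxaemia, bradycardia, arrhythmias | the RM |
| Efficacy and Safety Issues, severe instability (hypotension or arrhythmias) | the patient, from the study |

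The last row claims to repeat an earlier statement. No earlier section says that instability during the RM ends study participation; the exclusions that do so end at deflation. The next sentence in Efficacy and Safety Issues expects pressure to improve once the RM is removed, so the rule is about children receiving the RM. Removal is therefore after allocation and one-sided.

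**2. Which analysis branch applies.** With 1, 2 or 3 of 30 removed, completion is 29/30 = 96.7%, 28/30 = 93.3% or 27/30 = 90.0%. Each is naturally read as the great majority, so per protocol applies and these children leave the comparison.

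**3. The plan's own figures.** Sample size determination gives a difference of 20% of the mean, an SD of 15% of the mean, two-sided alpha 0.05 and power 0.90. The effect size is 0.20/0.15 = 1.33. With the noncentral t distribution, power is 0.877 at 12 per group and 0.903 at 13 per group, so the stated 13 per group is reproduced. Power is 0.94 for 15 v 15 and 0.91 for 12 v 15. Loss of power is not the problem; selection is.

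**4. Possible bias.** Assume no true RM effect and an SD of 15% of the mean. Remove the k of 15 RM patients ranked worst on an instability score that has correlation rho with low post-RM compliance, and compare the rest with 15 controls by a two-sided t-test (100,000 simulated trials). At rho = 1 the RM mean rises by 0.123, 0.229 or 0.328 SD for k = 1, 2 or 3. Multiplying by 15% gives 1.85%, 3.44% or 4.92% of the mean.

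| k removed | rho = 0: bias; error | rho = 0.3 | rho = 0.5 | rho = 1 |
|---|---|---|---|---|
| 1 | 0; 0.050 | 0.54%; 0.052 | 0.94%; 0.055 | 1.85%; 0.071 |
| 2 | 0; 0.050 | 1.05%; 0.054 | 1.71%; 0.061 | 3.44%; 0.107 |
| 3 | 0; 0.049 | 1.48%; 0.057 | 2.44%; 0.072 | 4.92%; 0.158 |

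The worst entry is 4.92/20 = about a quarter of the target difference. Both k and rho are assumptions; the documents give neither.

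**5. Effect of keeping these children.** If the RM truly adds 20% and a stopped RM adds nothing (assumption), the expected difference as randomised is 20 x (15 - k)/15 = 18.7%, 17.3% or 16.0% for k = 1, 2 or 3. Divided by the 15% SD, that is 1.24, 1.16 or 1.07 instead of 1.33.

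**6. Recording.** Appendices 3 to 6 and Table 1 contain no field for a pressure, heart rate, saturation or event during the RM, and none for whether the RM was completed. Beat-to-beat arterial pressure is available at that moment. Vasoconstrictors are given only if hypotension persists after the RM ends, so that field misses transient falls.

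**The case against.** A reader might infer that efficacy **is** inflated. The documents do not support that.

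- There is no bias if instability is unrelated to compliance, and at correlations of 0.3 to 0.5 it is 0.5% to 2.4% of the mean for up to three removals.
- The protocol links hypotension to chest wall compliance and oxygenation response, not directly to the primary endpoint, and adds that hypotension during the RM suggests volume depletion. A link remains plausible, since the Limitations section says chest wall compliance may affect the measured compliance, but its strength is unknown.
- The protocol calls recruitment generally well tolerated, and the children are ASA 1-2 without heart or lung disease. Three of 15 may be too many.
- Under the LOCF branch a removed child carries forward a pre-RM value, which would tend to dilute the effect. That branch, however, needs many non-completers.

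A reader might also infer that harm is hidden. That is too strong as well. Adverse Events requires RM complications, hypotension, bradycardia and desaturation to be recorded, End of Study adds events during the hospital stay, and vasoconstrictor need is tabulated. Nothing says that removed children leave the safety tables; equally, nothing says that they stay.

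What survives is the conflict between the two sections, the one-sided removal that one of them permits, and the lack of a form field for the RM itself.

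**Conclusion.** The point holds as a contradiction in the text and a risk of bias, not as demonstrated inflation. One section ends therapy, the other ends study participation, and they must be reconciled. On the second reading, with the per-protocol default, a few RM patients could leave the primary comparison and no control could leave by the same route.

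The direction favours the RM if unstable children have lower compliance. For 1 to 3 of 15 removed, the size runs from zero to about 1.9% to 4.9% of the mean, with two-sided error of about 7% to 16% at the extreme. That extreme requires the removed children to be exactly those with the lowest compliance. On safety, events are to be recorded, but the forms give no place for values or events during the RM.

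**What to change.** Leave the criteria for stopping the RM as they are; nothing here bears on them.

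1. In both Removal of Patients from Therapy and Efficacy and Safety Issues, state that a child whose RM is stopped stays in the study, is measured at T5 and T6, and remains in the safety tables.
2. In Data Presentation Plan, Flow chart, state that the primary analysis includes all randomised patients with a T5 value in their assigned group, whether or not the RM was completed. Without this, the per-protocol default could still drop the same children.
3. Optional: record whether the RM was completed or stopped, and the lowest systolic and mean pressure, heart rate and SpO2 over a fixed window of equal length in both arms, starting 3 minutes after deflation. The window cannot simply run to T5, because T5 has no clock time in controls. Keep these entries on a form held by the unblinded investigator, since a completed/stopped entry would reveal the allocation to the blinded recorder.

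The cost is a few sentences and, if item 3 is adopted, one short form filled from monitoring already in place. The downside is an efficacy estimate that may be slightly less favourable, as the dilution figures show, with some loss of power.
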